5.3.3. Medical History

Medical history will be coded according to the Medical Dictionary for Regulatory Activities (MedDRA, the most up-to-date version at the time of analysis). Medical history will be summarized by system organ class and preferred term for each cohort and for all patients and will be listed as well.

5.3.4. Prior/Concomitant Therapy

5.3.4.1. Prior Anticancer Therapy

Prior anticancer surgery and prior radiation therapy will be summarized for each cohort and for all patients based on All Treated Population. For prior surgery, the number and percentage of patients with at least one anticancer surgery for primary disease will be presented. The type of surgery will be summarized. The time from prior surgery to the first dosing date will be summarized. For prior radiation therapy, the number and percentage of patients with at least one radiation therapy for primary disease will be presented. The intention of radiotherapy, radiation therapy site location, duration of radiation therapy and time from end date of radiation therapy to first dosing date will be summarized.

For prior systemic anticancer therapy, the number and percentage of patients with at least one prior systemic anticancer therapy for primary disease will be presented. The treatment type and therapy type will be summarized. Patients' best response (CR, PR, SD, PD, and NE) to the therapy will be summarized. The duration of systemic anticancer therapy and time from end date of systemic anticancer therapy to first dosing date will be summarized. The reason for therapy discontinuation will also be summarized. The above analysis will be repeated for each treatment type (adjuvant therapies, neoadjuvant therapies, therapies for advanced/metastatic disease) in separate tables. The number of patients with prior systemic regimens will be summarized.

Prior anticancer therapy will be coded with World Health Organization (WHO) Drug Dictionary (most up-to-date version at the time of analysis) and will be summarized by ATC level 2 (Therapeutic Main Group) and ATC level 4 (Chemical/Therapeutic Subgroup) for each cohort and for all patients based on All Treated Population. Medications and therapies will be sorted in descending order of frequency of ATC level 2 and ATC level 4 within ATC level 2 in the total column. A patient will be counted only once within each level of summarization if the patient has taken a medication more than once.

All collected information for prior surgery, prior-radiation therapy, and prior anticancer therapy will be listed.

5.3.4.2. Concomitant Medication and Therapy

Medications started prior to the first dose of study drug and continued into the treatment period are considered as concomitant medications and therapies. Medications taken on or after the first dose of study drug through 30 days after the last dose of study drug are considered as concomitant medications and therapies.

Concomitant medications will be coded with World Health Organization (WHO) Drug Dictionary (most up-to-date version at the time of analysis). Concomitant medications will be summarized by ATC level 2 (Therapeutic Main Group) and ATC level 4 (Chemical/Therapeutic Subgroup) for each cohort and for all patients based on All Treated Population. Medications will be sorted in descending order of frequency of ATC level 2 and ATC level 4 within ATC level 2 in the total column. A patient will be counted only once within each level of summarization if the patient has taken a medication more than once. Agents and medications will be reported using the generic name. All concomitant medications will be listed.

In addition, the number and percentage of patients who received concomitant medications for management of hyperphosphatemia will be summarized by medication class and generic term for each cohort and for all patients. Total duration of medications (excluding overlaps) for management of hyperphosphatemia will be also summarized.

5.4. Efficacy Analyses

Unless otherwise specified, all efficacy analyses will be performed for each cohort based on patients in All Treated Population.

5.4.1. Primary Efficacy Analyses

The primary endpoint is ORR per RECIST 1.1. The description of each efficacy endpoint is provided in Table 3. Tumor assessments will be performed as per Table 1. The evaluation of endpoints will be based on the Investigator or local radiologist.

Table 3. Efficacy Endpoint Definitions

Endpoint	Definition
ORR	The proportion of patients experiencing a best overall response of PR or CR
DCR	the proportion of patients experiencing a best overall response of SD, PR, or CR
DoR	The time from the first documentation of response (CR or PR) to the first documentation of objective tumor progression or death due to any cause, whichever occurs first
PFS	The time from first dose of study therapy to the date of death (any cause) or disease progression, whichever occurs first
OS	The time from the date of first dose to the death date

Abbreviations: ORR=objective response rate; CR=complete response; PR=partial response; SD=stable disease; DCR=disease control rate; DoR=duration of response; OS=overall survival; PFS=progression-free survival

ORR per RECIST 1.1 will be summarized by a binomial response rate for each cohort. ORR per RECIST 1.1 will be calculated based on the best overall response recorded from the start of treatment until progression disease or start of subsequent new anticancer treatment. The overall

response can be derived based on target lesion response, non-target lesion response and the emergence of new lesion for patients with measurable disease at baseline. Table 4 presents the rules to derive the overall response.

The best overall response, CR and PR, will be confirmed with at least 4 weeks intervals of two consecutive time points. A minimum of 6-week interval between initial treatment (first dosing date) and tumor measurement is required for SD. The confirmation rule of the best overall response per RECIST 1.1 is shown in Table 5.

The exact 2-sided 90% CI based on Clopper–Pearson methodology will be derived for ORR.

For Cohort A, the null hypothesis (ORR of 35%) will be rejected if at least 12 responders observed out of 20 patients.

For Cohort B, the null hypothesis (ORR of 25%) will be rejected if at least 9 responders observed out of 20 patients.

Table 4. Overall Response Assessment with Target/Non-target Lesion and New Lesions

Target Lesions	Non-target Lesions	New Lesions	Overall Response
CR	CR	No	CR
CR	Non-CR/Non-PD or Not all evaluated	No	PR
PR	Non-PD or Not all evaluated	No	PR
SD	Non-PD or Not all evaluated	No	SD
Not all evaluated	Non-PD	No	Not evaluable
PD	Any	Yes or No	PD
Any	PD	Yes or No	PD
Any	Any	Yes	PD

Table 5. Confirmation Rules for Overall Response of PR and CR per RECIST 1.1

Earlier Response (to be confirmed)	Later Response (confirmation)	Confirmed Response
CR	CR	CR
CR	Not CR or missing	SD
PR	CR or PR	PR
PR	SD or PD or missing	SD
PR	SD and then PR (only one SD in between)	PR
SD	n/a – no confirmation needed	SD
PD	n/a – no confirmation needed	PD

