The 6 patients initially enrolled in the safety lead-in will also be assigned to the respective cohort based on *FGFR* alteration, such that each cohort will contain a minimum of 20 and a maximum of 26 patients.

Number of Patients:

The study will enroll approximately 46 patients with advanced or metastatic UC: 6 patients in the safety lead-in, 20 patients with tumors positive for any *FGFR3* mutation or *FGFR* fusion alterations (Cohort A) and 20 patients with other FGFR aberrations or wild-type (WT) tumors (Cohort B).

Entry Criteria:

Inclusion Criteria

1. Histologically confirmed advanced or metastatic UC for patients who have not received systemic treatment for advanced metastatic disease. For patients who received prior adjuvant/neoadjuvant chemotherapy or chemo-radiation for urothelial carcinoma, a treatment-free interval >12 months between the last treatment administration and the date of recurrence is required in order to be considered treatment-naïve in the metastatic setting.
 - a. In safety lead-in: enrollment regardless of FGFR status
 - b. Cohort A: must have an *FGFR3* mutation or *FGFR1-4* fusion/rearrangement
 - c. Cohort B: all other patients with UC (including patients with other FGFR or non-FGFR genetic aberrations and patients with WT [nonmutated] tumors)
2. Unfit for or intolerant to standard platinum-based chemotherapy as defined by any one of the following criteria:
 - a. Chronic kidney disease characterized by the estimated creatinine clearance rate (eCCr) per Cockcroft-Gault formula of <60 mL/min or estimated glomerular filtration rate (eGFR) of <60 mL/min/1.73 m², corresponding to NCI-CTCAE v.5.0 Grade ≥ 2
 - b. Impaired hearing (measured by audiology) of >25 dB at two contiguous test frequencies in at least one ear, corresponding to NCI-CTCAE v.5.0 Grade ≥ 2
 - c. Peripheral sensory neuropathy Grade ≥ 2 by NCI-CTCAE v.5.0
 - d. Patient refusal
 - e. In the opinion of the Investigator, the patient is considered ineligible to receive any platinum-based chemotherapy
3. Be willing and able to provide written informed consent for the trial.
4. Be ≥ 18 years of age.
5. Have an Eastern Cooperative Oncology Group (ECOG) performance status (PS) of 0 to 1.
6. Adequate organ function as defined by the following criteria:
 - a. Absolute neutrophil count (ANC) $\geq 1.5 \times 10^9$ /L
 - b. Platelet count $\geq 100,000/\text{mm}^3$

- c. Hemoglobin ≥ 9.0 g/dL

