11.5.3.1. Primary Efficacy Analysis

ORR per RECIST 1.1 will be estimated with the exact 2-sided 90% confidence interval (CI). Only the evaluations before disease progression or initiation of new anticancer treatment will be used for the estimation.

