Please note: at each safety interim analysis, the combination of futibatinib and pembrolizumab will be considered intolerable if the incidence of unacceptable toxicity including dose-limiting toxicity (as defined in Section 5.2 “Definition of Dose-Limiting Toxicity” of the protocol) is $\geq 33\%$. If the combination is determined to be intolerable, the study may continue with a reduced dose of futibatinib (16 mg QD) if medically appropriate in the opinion of the investigator and Sponsor.

Of note, the 6 patients initially enrolled in the safety lead-in period will also be assigned to the respective cohort based on *FGFR* alteration, such that each cohort will contain a minimum of 20 and a maximum of 26 patients.

The detailed study schedule is shown in Table 1.

Table 1. Schedule of Events

Evaluations on Day 1 (D1) of a cycle should be performed within 24 hours prior to dosing, unless otherwise noted. Procedures already performed during the screening period within 72 hours prior to dosing do not need to be repeated on Cycle 1D1 (C1D1). The End of Treatment (EOT) visit must be performed 0-7 days after a decision is made to discontinue study treatment (for patients who discontinue at a planned study visit, that visit may be considered the EOT visit if all assessments required at EOT are performed).

Evaluation	Screening (Within 28 days of 1 st dose)	Treatment Period (1 cycle =21 days)					Safety Follow-up	Survival Follow-up Period (every 12±2 weeks)	Notes			
		Cycle 1		Cycle ≥2								
		D1 (-1 day)	D8 (-1 day)	D15 (-1 day)	D1 (-1 day)	End of Cycle (±7days)						
Written informed consent	X									Written informed consent will be obtained prior to any study-related assessments or procedures.		
Review eligibility criteria	X											
Demographics/medical history	X											
Review of baseline signs and symptoms	X											
Prior & concomitant medications, AE assessments							►			Collect from the time main informed consent is signed through 90 days after administration of the last dose of study therapy or until the start of new anticancer therapy, whichever is earlier.		
Physical examination	X	X			X		X	X		Within 24 hours prior to dosing.		
Vital signs	X	X			X		X	X		Heart rate, blood pressure, body temperature, and respiration rate.		
Height and Weight	X	X			X		X	X		Height at screening only.		
ECOG performance status	X	X			X		X	X		Within 24 hours prior to dosing.		
12-Lead electrocardiogram		X			X		X	X				

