3.3. Determination of Sample Size

Approximately 20 patients will be enrolled in Cohort A. Sample size considerations are based on differentiating a historical control ORR per RECIST 1.1 of 35% or less, with a target ORR per RECIST 1.1 of 65%. Assuming the true ORR per RECIST 1.1 is 65%, the cohort has an approximate 80% power to reject the null hypothesis that the true ORR per RECIST 1.1 is $\leq 35\%$, considering a 2-sided alpha of 10%. With a sample size of 20, observing at least 12 responders will have a 90% confidence interval (CI) lower bound excluding 10% (ORR per RECIST 1.1 of 60% with 90% CI (39.4% - 78.3%)).

Approximately 20 patients will be enrolled in Cohort B. Sample size considerations are based on differentiating a historical control ORR per RECIST 1.1 of 25% or less, with a target ORR per RECIST 1.1 of 50%. Assuming the true ORR per RECIST 1.1 is 50%, the cohort has an approximate 80% power to reject the null hypothesis that the true ORR per RECIST 1.1 is $\leq 25\%$, considering a 2-sided alpha of 10%. With a sample size of 20, observing at least 9 responders will have a 90% CI lower bound excluding 10% (ORR per RECIST 1.1 of 45% with 90% CI (25.9% - 65.3%)).

Note that the first 6 patients will be enrolled into the initial safety lead-in period without regard for FGFR alteration status. The 6 patients will also be assigned to Cohorts A or B based on *FGFR* alteration, such that each cohort will contain a minimum of 20 and a maximum of 26 patients.

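### The primary rejection rules exist only for 20-patient cohorts, but the plan puts 20 to 26 patients in each cohort, so at about 46 treated at least one primary test has no valid stated rule

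*SAP*

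**What the plan says.** SAP 5.4.1 states the primary test as two responder counts. Its rule for Cohort A is that "the null hypothesis (ORR of 35%) will be rejected if at least 12 responders observed out of 20 patients". The Cohort B rule has the same form, with a count of 9 in 20 and a null of 25%. The sentence before them plans an exact (Clopper-Pearson) 2-sided 90% confidence interval for ORR, and protocol 11.5.3.1 plans the same interval as an estimate.

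Four other statements fix the number of patients to which the test applies:

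- SAP 3.1: "the 6 patients initially enrolled in the safety lead-in period will also be assigned to the respective cohort".
- SAP 3.3: this is done "such that each cohort will contain a minimum of 20 and a maximum of 26 patients".
- SAP 5.4: "all efficacy analyses will be performed for each cohort based on patients in All Treated Population".
- Protocol synopsis, Number of Patients: "The study will enroll approximately 46 patients with advanced or metastatic UC", made up of 6 in the lead-in and 20 in each cohort.

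SAP 3.3 and protocol 11.1 give a 2-sided alpha of 10%, null and target ORRs of 35% and 65% (A) and 25% and 50% (B), and power of about 80%. Only one kind of statement links the counts to the interval. For Cohort A, SAP 3.3 says that "observing at least 12 responders will have a 90% confidence interval (CI) lower bound excluding 10" percent, and it uses the same 10% for Cohort B.

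**The concern.** Forty-six patients cannot be divided 20 and 20, so at the planned size at least one primary test falls outside the written rule. Nothing limits the test to 20 patients, and doing so would contradict SAP 5.4. Nothing makes the confidence interval the decision criterion either, and the one comparison offered is with 10%, which is neither null.

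For a cohort larger than 20, a reader could keep the counts (12 and 9), keep the proportions (60% and 45%), or count only 20 patients. A fourth option, the exact test at the actual n, can be inferred but is not written. These give different verdicts on the same data. Treatment is open-label and response is assessed by the investigator or local radiologist, so the choice could be made with responses in view. If the counts are kept, the trial could declare a null rejected while its own 90% interval still contains it.

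**Working it through.** **Inputs.** Nulls 35% and 25%, targets 65% and 50%, 2-sided alpha 10% (5% in the upper tail): SAP 3.3. Counts 12 and 9: SAP 5.4.1. Cohort size 20 to 26: SAP 3.3. Total of about 46: protocol synopsis.

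**Formulas.** With X responders among n patients and X ~ Bin(n, p):

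- type I error of a cut-off r = P(X ≥ r | n, null);
- power = P(X ≥ r | n, target);
- lower limit of the exact 90% interval for x responders = 5th percentile of Beta(x, n − x + 1). It exceeds the null exactly when the upper-tail probability at x is below 5%.

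**Step 1: the plan's figures at n=20.** The exact intervals are 39.4% to 78.3% for 12/20 and 25.9% to 65.3% for 9/20, as SAP 3.3 states. P(X ≥ 12 | 20, 0.35) = 1.96%, and 11 would give 5.3%. P(X ≥ 9 | 20, 0.25) = 4.1%, and 8 would give 10.2%. So 12 and 9 are the correct cut-offs at n=20. Exact power there is 76.2% (A) and 74.8% (B).

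**Step 2: the rules at n=20 to 26.** Each cell gives the cut-off, then type I error / power. The proportion rule rounds 0.60n or 0.45n up.

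| n | A: fixed 12, error (90% lower limit of 12/n) | A: exact | A: 60% | B: fixed 9, error (90% lower limit of 9/n) | B: exact | B: 45% |
|---|---|---|---|---|---|---|
| 20 | 2.0% (39.4%) | 12: 2.0 / 76.2% | 12: 2.0 / 76.2% | 4.1% (25.9%) | 9: 4.1 / 74.8% | 9: 4.1 / 74.8% |
| 21 | 3.1% (37.2%) | 12: 3.1 / 83.8% | 13: 1.1 / 70.6% | 5.6% (24.5%) | 10: 2.1 / 66.8% | 10: 2.1 / 66.8% |
| 22 | 4.7% (35.3%) | 12: 4.7 / 89.3% | 14: 0.6 / 64.7% | 7.5% (23.3%) | 10: 3.0 / 73.8% | 10: 3.0 / 73.8% |
| 23 | 6.8% (33.5%) | 13: 2.8 / 85.8% | 14: 1.0 / 74.1% | 9.6% (22.2%) | 10: 4.1 / 79.8% | 11: 1.5 / 66.1% |
| 24 | 9.4% (31.9%) | 13: 4.2 / 90.6% | 15: 0.6 / 68.7% | 12.1% (21.2%) | 11: 2.1 / 72.9% | 11: 2.1 / 72.9% |
| 25 | 12.5% (30.5%) | 14: 2.6 / 87.5% | 15: 0.9 / 77.1% | 14.9% (20.2%) | 11: 3.0 / 78.8% | 12: 1.1 / 65.5% |
| 26 | 16.2% (29.2%) | 14: 3.8 / 91.7% | 16: 0.5 / 72.2% | 18.0% (19.4%) | 11: 4.0 / 83.7% | 12: 1.6 / 72.1% |

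The fixed count contradicts the SAP's own interval from n=23 in Cohort A and from n=21 in Cohort B.

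**Step 3: splits of 46.** Type I error with fixed counts, A / B: 20/26, 2.0 / 18.0%; 21/25, 3.1 / 14.9%; 22/24, 4.7 / 12.1%; 23/23, 6.8 / 9.6%; 24/22, 9.4 / 7.5%; 25/21, 12.5 / 5.6%; 26/20, 16.2 / 4.1%. At least one cohort exceeds 5% in every split. The same holds for every split of 43, 44 or 45 treated with 20 to 26 per cohort. At 40, 41 and 42 treated, only the splits 20/20, 21/20 and 22/20 (A/B) keep both at or below 5%.

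**Step 4: how often the readings disagree.** Two rules disagree in a cohort when the responder count lies from the lower cut-off up to one below the higher. For fixed 12 against 60% in Cohort A at n=26, that is 12 to 15 responders. The probability that at least one cohort disagrees is 1 − (1 − zone probability in A)(1 − zone probability in B), with the cohorts independent. Ranges are over the seven splits of 46:

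| True ORR (A, B) | Fixed counts v. proportions | Fixed counts v. exact | Exact v. proportions |
|---|---|---|---|
| Nulls (35%, 25%) | 13.0–16.5% | 9.3–14.0% | 1.6–4.4% |
| Targets (65%, 50%) | 24.1–39.3% | 6.8–22.6% | 10.3–24.7% |
| Midway (50%, 37.5%) | 45.2–55.8% | 29.7–41.6% | 13.3–27.3% |

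The midway rates are an assumption made here for illustration; they are not in the documents.

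**The case against.** The strongest reply is that the rule is implied. The nulls, the alpha and the exact 90% interval are all pre-specified. Together they determine one boundary at any n, and at n=20 that boundary is exactly 12 and 9. On this view the counts are the n=20 case of an interval test, and one sentence of generalisation is missing. The fair comparison is then fixed counts against the exact boundary, where disagreement is smaller (9.3–14.0% under the nulls, 6.8–22.6% under the targets). The synopsis also says efficacy will be summarised descriptively, the documents tie no decision to rejection, and the interval will be reported, so a wrong declaration would be visible. The largest errors need all six lead-in patients to fall in one cohort, and 12 remains the exact cut-off in Cohort A at n=21 and 22.

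Much of this stands: a boundary can be derived, and the smaller figures are the right ones if it is taken as the intended rule. It does not remove the point. The SAP never names the interval as the criterion, and its one comparison uses 10%. Its literal counts give the opposite verdict to its interval over most of the planned range of n. The word "descriptively" in the synopsis does not cancel a SAP sentence saying that a null will be rejected. The Cohort A exception does not help at 46 treated: with 21 or 22 in A, B has 25 or 24 and an error of 14.9% or 12.1%.

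**Conclusion.** The concern holds. At the planned size, at least one of the two primary tests has no valid stated rule, and the natural carry-over of the counts breaks the 5% upper-tail error in at least one cohort for every split of 43 to 46 treated. The excess ranges from slight (B at n=21, 5.6%) to more than threefold (A 16.2%, B 18.0% at n=26). Carrying over the proportions controls the error. At n=21 to 26 it gives power of 64.7–77.1% in Cohort A against 83.8–91.7% with the exact cut-offs, and 65.5–73.8% in Cohort B against 66.8–83.7%. In Cohort B the proportion rule coincides with the exact rule at n=21, 22 and 24.

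This assumes that about 46 patients are treated with 20 to 26 per cohort, that responses are binomial and, for the disagreement probabilities, that the cohorts are independent. Because this is the decision rule for the primary endpoint, it should be corrected before responses are analysed.

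**What to change.** In SAP 5.4.1, replace the two counts with: H0 is rejected if the lower limit of the exact 2-sided 90% confidence interval for ORR, in all treated patients of the cohort, exceeds 35% (Cohort A) or 25% (Cohort B). Tabulate the matching cut-offs:

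- Cohort A: at least 12 for n=20–22, 13 for n=23–24, 14 for n=25–26.
- Cohort B: at least 9 for n=20, 10 for n=21–23, 11 for n=24–26.

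In SAP 3.3, protocol 11.1 and the matching synopsis text, replace the 10% that the lower bound is said to exclude with 35% for Cohort A and 25% for Cohort B.

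The cost is wording only: no extra patients, and no new analysis, since the interval is already planned. The required counts rise in larger cohorts. Because counts are discrete, Cohort B power dips to 66.8% at n=21, 73.8% at n=22 and 72.9% at n=24, against 74.8% at n=20. It is higher than at n=20 for the other sizes, and Cohort A gains power at every n above 20.

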5.4.2. Secondary Efficacy Analyses

The secondary efficacy endpoints are ORR per iRECIST, DCR per RECIST 1.1, DCR per iRECIST, DoR per RECIST 1.1, DoR per iRECIST, PFS per RECIST 1.1, PFS per iRECIST, and OS. The description of each efficacy endpoint is provided in Table 3. Tumor assessments will be performed as per Table 1. The evaluation of endpoints will be based on the Investigator or local radiologist.

ORR per RECIST 1.1, ORR per iRECIST, DCR per RECIST 1.1, and DCR per iRECIST will be calculated based on the best overall response. The exact 2-sided 95% CI based on Clopper–Pearson methodology will be derived for DCR. The 95% CI of ORR will also be calculated conventionally.

PFS per RECIST 1.1 and OS will be analyzed using Kaplan–Meier product-limit estimates for each cohort. Patients who are alive and progression-free as of the data cut-off date will be censored at their last evaluable tumor response assessment prior to initiation of any new anticancer treatment. Patients who start subsequent anticancer therapy without a prior reported progression will be censored at the last tumor assessments prior to initiation of the subsequent anticancer therapy. Median PFS per RECIST and OS will be presented with 2-sided 95% CI if estimable. The cumulative PFS and OS will be plotted over time by cohort. The censoring rule for PFS per RECIST and OS is in Table 6 and Table 8, respectively.

PFS per iRECIST will be analyzed using Kaplan–Meier product-limit estimates for each cohort. Patients who are alive and progression-free as of the data cut-off date will be censored at their last evaluable tumor response assessment prior to initiation of any new anticancer treatment. Patients who start subsequent anticancer therapy without a prior reported progression will be censored at the last tumor assessments prior to initiation of the subsequent anticancer therapy. Median PFS per iRECIST will be presented with 2-sided 95% CI if estimable. The cumulative PFS per iRECIST will be plotted over time by cohort.

- The event date to be used for PFS per iRECIST is the first date of iUPD at which iCPD is confirmed at the next assessment.
- If iUPD occurs, but is disregarded because of later iSD, iPR, or iCR, that the iUPD date is not be used as the progression event date.
- If iCPD is not confirmed and there is no subsequent iSD, iPR, or iCR, then the iUPD date is used as the progression event date in the following scenarios: if the patient stops protocol treatment because they were not judged to be clinically stable, or no further response assessments are done (because of patient refusal, protocol noncompliance, or patient death); the next timepoint responses are all iUPD, and iCPD never occurs; or the patient dies from their cancer.
- The censoring rule for PFS per iRECIST is in Table 7, respectively.

DoR per RECIST 1.1 will be evaluated only in patients with objective response of CR or PR. DoR per RECIST 1.1 will be analyzed using Kaplan–Meier product-limit estimates for each cohort. Patients who are alive and progression-free as of the data cut-off date will be censored at their last evaluable tumor response assessment prior to initiation of any new anticancer treatment. Patients who start subsequent anticancer therapy without a prior reported progression will be censored at the last tumor assessments prior to initiation of the subsequent anticancer therapy. Median DoR per RECIST 1.1 will be presented with 2-sided 95% CI if estimable. The cumulative DoR per RECIST 1.1 will be plotted over time by cohort. The censoring rule for DoR per RECIST 1.1 is in Table 9.

DoR per iRECIST will be evaluated only in patients with objective response of CR or PR. DoR per iRECIST will be analyzed using Kaplan–Meier product-limit estimates for each cohort. Patients who are alive and progression-free as of the data cut-off date will be censored at their last evaluable tumor response assessment prior to initiation of any new anticancer treatment. Patients who start subsequent anticancer therapy without a prior reported progression will be censored at the last tumor assessments prior to initiation of the subsequent anticancer therapy. Median DoR per iRECIST will be presented with 2-sided 95% CI if estimable. The cumulative DoR per iRECIST will be plotted over time by cohort.

- The start date to be used for DoR per iRECIST is the first date of iCR or iPR for which the first evaluation is confirmed at the next assessment.
- The event date to be used for DoR per iRECIST is the first date of iUPD for which iCPD is confirmed at the next assessment.
- If iUPD occurs, but is disregarded because of later iSD, iPR, or iCR, that the iUPD date is not be used as the progression event date.

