8.2. Use of iRECIST to Guide Treatment Decisions

Until radiographic disease progression based on RECIST 1.1, there is no distinct iRECIST assessment. Upon documentation of PD per RECIST 1.1, patients who are clinically stable should not be discontinued until progression is confirmed by the Investigator, working with local radiology, according to the rules outlined in [Appendix D](#).

Clinical stability is defined as the following:

- Absence of symptoms and signs indicating clinically significant progression of disease
- No decline in ECOG performance status
- No requirements for intensified management, including increased analgesia, radiation, or other palliative care

Any patient deemed **clinically unstable** should be discontinued from study treatment at site-assessed first radiologic evidence of PD, and is not required to have repeat tumor imaging for confirmation of PD by iRECIST.

If the Investigator decides to continue treatment, the patient may continue to receive study treatment and the tumor assessment should be repeated 4 to 8 weeks later to confirm PD by iRECIST, per Investigator assessment. Images should continue to be sent in to the Sponsor.

If repeat imaging does not confirm PD per iRECIST, as assessed by the Investigator, and the patient continues to be clinically stable, study treatment may continue and follow the regular imaging schedule. If PD is confirmed, patients will be discontinued from study treatment.

If a patient has confirmed radiographic progression (iCPD) as defined in [Appendix D](#), study treatment should be discontinued; however, if the patient is achieving a clinically meaningful benefit, an exception to continue study treatment may be considered following consultation with the Sponsor. In this case, if study treatment is continued, tumor imaging should continue to be performed.

A description of the adaptations and iRECIST process is provided in [Appendix D](#), with additional details in the iRECIST publication ([Seymour et al. 2017](#)). A summary of imaging and treatment requirements after first radiologic evidence of progression is illustrated in [Figure 2](#).

[figure not shown]

Figure 2: Imaging and treatment for clinically stable patients treated with pembrolizumab after the first radiologic evidence of progression per RECIST 1.1

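### DoR per iRECIST starts only at a response confirmed on the very next scan, while SAP Table 5 confirms PR–SD–PR, so the same pre-progression scans can give a later iRECIST start date or none

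*SAP*

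**What the plan says.** Five statements bear on when a response starts.

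- **DoR definition.** SAP Table 3 (section 5.4.1) gives one definition without separating the two criteria: "The time from the first documentation of response (CR or PR) to the first documentation of objective tumor progression or death due to any cause". The earlier of the two events counts.
- **RECIST 1.1 confirmation, table.** SAP 5.4.1 states: "The confirmation rule of the best overall response per RECIST 1.1 is shown in Table 5". In that table, an initial PR followed by "SD and then PR (only one SD in between") is a confirmed PR.
- **RECIST 1.1 confirmation, narrative.** The same section says: "The best overall response, CR and PR, will be confirmed with at least 4 weeks intervals of two consecutive time points".
- **iRECIST DoR start.** SAP 5.4.2 uses the "first date of iCR or iPR for which the first evaluation is confirmed at the next assessment". It makes no allowance for an intervening stable scan.
- **Relation of the two criteria.** Protocol 8.2, repeated in Appendix D: "Until radiographic disease progression based on RECIST 1.1, there is no distinct iRECIST assessment".

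The SAP has no response-confirmation table for iRECIST. Its Table 10 (DoR per iRECIST) gives end-date rules only. Protocol 8.1.4 requires CR and PR to be confirmed but does not say how, and Protocol 8.1.3 leaves response assessment to the SAP.

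**The concern.** Before RECIST 1.1 progression a patient has one set of scans and one set of time-point calls. A response that begins in that period should therefore have one start date, whichever criterion is later used to date progression. The SAP's two rules agree when the scan after the first PR is PR or CR. They part when a single SD comes between two PRs: Table 5 counts the first PR, and the iRECIST bullet, taken at its word, does not.

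For such a patient the iRECIST DoR is shortened by the start rule alone, or cannot be computed. No reason is given for a stricter iRECIST start, and no instruction covers a responder without a start date, so the programmer would have to choose.

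**Working it through.** **Scan interval.** The protocol's cycle is 21 days, with imaging every 3 cycles: 3 × 21 = 63 days = 9 weeks. This reproduces the 9-week interval in Protocol 3.2.3. Scans fall at weeks 9, 18, 27, 36 and 45, each ±7 days.

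**Can the pattern occur?** Take a baseline target sum of 100 mm, then 68, 74 and 69 mm, using Protocol Table 11.
- 68 is at or below 70 (a 30% decrease), so PR.
- 74 is above 70. Its rise from the nadir is 6/68 = 8.8%, below the 20% needed for PD, so SD.
- 69 is at or below 70, so PR.

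Ordinary measurement variation near the 30% boundary is enough.

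**Rules applied.**
- RECIST 1.1: start at the first PR of a response confirmed under Table 5, including PR–SD–PR.
- iRECIST, literal: start at the first iPR or iCR for which the immediately following scan confirms it.

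| Scans from week 9 | RECIST 1.1 start | RECIST 1.1 DoR | iRECIST start | iRECIST DoR |
|---|---|---|---|---|
| PR, PR, PR, PD | 9 | 36 − 9 = 27 wk | 9 | 36 − 9 = 27 wk |
| PR, SD, PR, PR, PD | 9 | 45 − 9 = 36 wk | 27 | 45 − 27 = 18 wk |
| PR, SD, PR, PD | 9 | 36 − 9 = 27 wk | none | – |
| PR, SD, PR, SD, PD | 9 | 45 − 9 = 36 wk | none | – |
| PR, SD, PR, then cut-off | 9 | censored | none | – |

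Two assumptions sit behind the iRECIST columns. Where a duration is shown, the RECIST PD is an iUPD that counts as the event. Where the start is shown as none, no iPR or iCR is confirmed later.

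**Size of the shift.** 27 − 9 = 18 weeks, two scan intervals. With ±1 week on each of the two scans the range is 16 to 20 weeks.

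**Cut-off case.** SAP 4.4 allows the final analysis once all patients have stopped treatment or have at least 6 months' follow-up, about 26 weeks. A patient followed to between about week 27 and week 36 can have the response confirmed under Table 5 but no iRECIST start date yet.

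**Weight of one patient.** The documents give no frequency for PR–SD–PR, so one such patient per cohort is an assumption.
- Cohort of 20: expected responders 0.50 × 20 = 10 (Cohort B) and 0.65 × 20 = 13 (Cohort A). One patient is 1/10 = 10% or 1/13 = 7.7%.
- Cohort of 26, the stated maximum: 0.50 × 26 = 13 and 0.65 × 26 = 16.9. One patient is 1/13 = 7.7% or 1/16.9 = 5.9%.

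**The narrative rule.** If the consecutive-scan sentence in SAP 5.4.1 governed instead of the Table 5 row, the week 9 PR in rows 2 to 5 would be unconfirmed under RECIST 1.1 too, and the two start dates would agree. The divergence therefore depends on Table 5 being the operative rule, as SAP 5.4.1 says it is.

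**The case against.** **There is no formal contradiction.** Table 5 is headed as a RECIST 1.1 rule and the bullet is an iRECIST rule. Protocol 8.2 concerns time-point assessment and treatment decisions, not the dating of DoR. This stands: the SAP may set two rules. It does not explain why identical scans should start the same response on different dates.

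**The outlier may be Table 5.** The narrative in SAP 5.4.1 agrees with the iRECIST bullet and conflicts with the PR–SD–PR row. This stands as well, and it means that editing the bullet alone would leave the larger inconsistency in place.

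**The wording is loose.** For progression, the SAP 5.4.2 bullets require iCPD at the *next* assessment, while Tables 7 and 10 refer to *subsequent* ones. *Next* may be equally loose in the start-date bullet. That is possible, but nothing in the SAP relaxes it there.

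**Stronger readings that a reader might infer.**
- *That responders are excluded from DoR per iRECIST.* The SAP defines that set as patients with an objective response and nowhere removes one who lacks a start date. The handling is unstated.
- *That a RECIST-versus-iRECIST comparison is biased.* None is planned. The two are separate Kaplan–Meier estimates per cohort, and the protocol calls the efficacy summaries descriptive.
- *That cohort-level DoR must come out shorter under iRECIST.* An iUPD can resolve to iPR or iCR, so iRECIST may add responders or extend durations. The direction is known only for an individual record such as those above.
- *That the primary endpoint is affected.* The bullet does not enter ORR per RECIST 1.1. Only the separate conflict between the narrative and Table 5 touches it.

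**Conclusion.** The point holds on the literal text. A Table 5 responder with PR–SD–PR gets an iRECIST start date 18 weeks later (16 to 20 with visit windows) if the second PR is confirmed at the next scan. If that scan is not PR or CR, or cut-off comes first, there is no start date unless a later iPR or iCR is confirmed. No rule covers the second case.

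The reach is modest: one descriptive secondary endpoint, and a pattern of unknown frequency. Assuming one such patient, the share of a cohort's DoR set is about 8–10% at 10 or 13 responders out of 20, and about 6–8% if the cohort reaches 26. The result rests on Table 5 being the operative RECIST 1.1 rule and on *next* being read as written. It deserves correction because the SAP should fix the start date before programming.

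**What to change.** 1. **Settle one confirmation rule.** Reconcile the consecutive-scan sentence in SAP 5.4.1 with the PR–SD–PR row of Table 5. This choice can also change who counts as a responder for the primary ORR, so make it before responses are tabulated.
2. **Replace the iRECIST start-date bullet**, for example: *For a response that begins before RECIST 1.1 PD, the DoR start date per iRECIST is the date of the first CR or PR of a response confirmed under that same rule, and is identical to the RECIST 1.1 start date. For a response first seen after iUPD, it is the date of the first iCR or iPR that is subsequently confirmed.*
3. **State how iPR–iUPD–iPR is treated for confirmation.** Table 5 has no iUPD row and maps PR followed by PD to SD, so it cannot simply be carried over to iRECIST.

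If PR–SD–PR is retained, row 2 of the table above becomes 36 weeks under both criteria and rows 3 to 5 gain a week 9 iRECIST start. If the consecutive-scan rule is chosen instead, the start dates also agree. The cost is a short SAP edit and minor programming, with no new data collection.
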